4.2 Stopping Criteria

For Part 1, as each patient will receive several, ascending single doses, there are stopping criteria for which further dosing of an individual patient must be suspended, and also stopping criteria for the study to be considered by SRC.

For Part 2, as each patient will receive 9 days of study drug treatment (including 2 days of single-blind placebo and 7 days of DB active or placebo), there are dose-modification criteria and stopping criteria for individual patients, as well as stopping criteria for the study to be considered by SRC.

4.2.1 *Stopping Criteria for an Individual Participant in Part 1 (SAD)*

If the following events occur, as determined by investigator assessment, dosing of a patient must be suspended, AE/SAE forms completed as applicable, and the event reviewed by the SRC. The SRC may decide to perform selected unblinding pertaining to one or several periods for a given patient or recommend that further dosing of the patient be suspended. The following is a list of possible criteria for suspension of dosing of an individual and review of the data by the SRC:

- A patient has drug-related cardiac ischemia, as determined by investigator (Note: The whole context [ie, clinical symptoms, ECG, and cardiac biomarkers such as troponin, CK-MB, cardiac imaging, and coronary angiograms, if applicable] should be taken into account by the investigator in making that determination since patients enrolled in the study are likely to have an abnormal ECG and/or elevated and/or fluctuating troponin at Baseline in relation to their heart failure condition. This information will also be submitted for subsequent central adjudication).
- A patient has an increase in the maximal SET > 75 ms on 2 sequential TTE recordings based on site evaluations.
- A patient has clinically significant and drug-related changes in his/her vital signs that are persistent over a period of time such as a new arrhythmia, systolic BP < 90 or > 170 mm Hg, or HR < 40 or > 100 bpm. The diagnosis and clinical significance of a new arrhythmia will be adjudicated by the SRC as it relates to this stopping criterion, including core lab assessments as appropriate.
- A patient experiences a drug-related SAE (including, but not limited to, serious unexpected suspected adverse reactions [SUSARs] or coronary ischemic events).
- A patient has a QTc interval > 500 ms (Fridericia's correction, average of triplicate ECGs) not attributable to pacing or prolonged QRS duration.
- Any patient fulfills the criteria for potential drug-induced liver injury (Hy's Law). These include:
 - Aminotransferases (alanine aminotransferase [ALT] or aspartate aminotransferase [AST]) are > 3 times ULN with an associated elevation of total bilirubin (TBL) > 2 times ULN without evidence of hemolysis, or

- ALT or AST activity that is > 5 times ULN, or
- TBL > 3 times ULN.

- A patient has 2 successive echocardiograms that show a $> 50\%$ relative increase from Baseline in at least 2 contractility indices (LVSV [derived from LVOT-VTI], LVEF, or LVFS).

4.2.2 Criteria for Unscheduled SRC Review of the Study in Part 1 (SAD)

If any of the following events occur at any time during the study, an ad hoc SRC review will be performed. Dosing may be paused for SRC review; eg, in case of drug-related SAEs, SUSAR, or coronary ischemic events (see [Section 4.2.1](#)). Based on the review of the data, the SRC may decide to unblind selected patients, terminate the study, continue dosing the patients using a modified dose-escalation scheme, or continue the dosing of the patients.

- The dosing of 2 patients who received MYK-491 is suspended because they reached the individual stopping criteria. The SRC will adjudicate stopping criteria.
- During the planned review by the SRC after the initial 4 patients in Cohort 1, evidence of PD activity will be considered to have been observed and dose escalation will be terminated if there is a Baseline-corrected, group mean relative increase of $> 40\%$ in 2 successive timepoints in 2 contractility indices (LVSV [derived from LVOT-VTI], LVEF, LVFS) in patients receiving MYK-491. Placebo-adjusted evaluation may be considered. The study may continue with the enrollment of Cohort 2, but the daily doses to be administered will not be greater than the daily dose that demonstrated the PD activity that terminated dose escalation.
- Any patient receiving MYK-491 experiences a drug-related SAE (including, but not limited to, a SUSAR or coronary ischemic event) that has not also occurred in a patient receiving placebo.
- Two or more patients receiving MYK-491 have QTc prolongation defined as > 500 ms (Fridericia's correction, average of triplicate ECGs) not attributable to pacing or prolonged QRS duration.
- Any patient receiving MYK-491 fulfills the definition for Hy's law:
 - Aminotransferases (ALT or AST) are > 3 times ULN with an associated elevation of TBL > 2 times ULN without evidence of hemolysis, or
 - ALT or AST activity that is > 5 times ULN, or
 - TBL > 3 times ULN.

Note: Screening may continue during an unscheduled SRC meeting, and if dosing is paused, Screening windows may be extended until dosing resumes.

4.2.3 *Dose-Modification Criteria for an Individual Participant in Part 2 (MAD)*

If the following events occur, as determined by investigator assessment, dosing of a patient should be modified by skipping one dose of study drug and resuming dosing at a lower dose (25% to 50% lower). The lower dose to be administered for a given cohort will be determined by SRC and communicated along with starting dose. [REDACTED]

- An increase in the maximal SET > 75 ms on 2 sequential TTE recordings based on site evaluations
- A patient has 2 successive echocardiograms that show a > 50% relative increase from Baseline in at least 2 contractility indices (LVSV [derived from LVOT-VTI], LVEF, or LVFS).

Note: Day 3, predose echo in the morning should be used as Baseline for local site evaluation.

In addition, in case of an AE, DB treatment may be temporarily suspended, as determined by the investigator. In such cases, the Sponsor medical monitor should be contacted without delay.

4.2.4 *Stopping Criteria for an Individual Participant in Part 2 (MAD)*

If the following events occur, as determined by investigator assessment, dosing of a patient must be terminated, AE/SAE forms completed as applicable, and Sponsor should be informed without delay:

- Drug-related coronary ischemia, as determined by investigator
Note: Whole context ie, clinical symptoms, ECG, cardiac biomarkers such as troponin, CK-MB, cardiac imaging, and coronary angiograms, if applicable, should be taken into account by the investigator in making that determination since patients enrolled in the study are likely to have elevated and/or fluctuating troponin and/or abnormal ECGs at Baseline in relation to their heart failure condition. This information will also be submitted for subsequent central adjudication.
- The patient has clinically significant and drug-related changes in his/her vital signs that are persistent over a period of time such as a new arrhythmia, systolic BP < 90 or > 170 mm Hg, or HR < 40 or > 100 bpm. The diagnosis and clinical significance of a new arrhythmia will be adjudicated by the SRC as it relates to this stopping criterion.
- A patient experiences a drug-related SAE (including, but not limited to, SUSARs or coronary ischemic events).
- A patient has a QTcF interval > 500 ms (Fridericia's correction, average of triplicate ECGs) not attributable to pacing or prolonged QRS duration.
- Any patient fulfills the criteria for potential drug-induced liver injury (Hy's Law). These include:

- Aminotransferases (ALT or AST) are > 3 times ULN with an associated elevation of TBL > 2 times ULN without evidence of hemolysis, or
- ALT or AST activity that is > 5 times ULN, or
- TBL > 3 times ULN.

4.2.5 *Criteria for Unscheduled SRC Review of the Study in Part 2 (MAD)*

If any of the following events occur at any time during the study, an ad hoc SRC review will be performed. Dosing may be paused until SRC review; eg, in case of drug-related SAEs, SUSAR, or coronary ischemic events. Based on the review of the data, the SRC may decide to unblind selected patients, terminate the study, continue dosing the patients using a modified dose-escalation scheme or continue the dosing of the patients.

- Two patients in a cohort receiving MYK-491 reached individual dose-modification and/or stopping criteria. The SRC will adjudicate stopping criteria.
- Any patient receiving MYK-491 experiences a drug-related SAE (including, but not limited to, a SUSAR or coronary ischemic event) that has not also occurred in a patient receiving placebo.
- Any patient receiving MYK-491 fulfills the definition for Hy's law
 - Aminotransferases (ALT or AST) are > 3 times ULN with an associated elevation of TBL > 2 times ULN without evidence of hemolysis, or
 - ALT or AST activity that is > 5 times ULN, or
 - TBL > 3 times ULN.

Note: Screening and dosing may be paused or may continue during an unscheduled SRC meeting.

4.3 *Study Duration*

The overall expected study duration is approximately 24 months.

In Part 1 (SAD), each patient is expected to be in the study no more than 77 days: up to 28 days for Screening plus up to 42 days for dosing including 7 days for follow up after the last dose (or longer if clinically indicated). Patients returning for an additional dosing period in Cohort 1 may have prolonged participation. Patients will be resident at the clinical site for each dosing period, each consisting of check-in on Day -1, dosing the following morning (Day 1) followed by \sim 24 hours of serial PD and \sim 48 hours of serial PK assessments, followed by discharge the following morning (Day 3). An additional outpatient plasma PK sample will be taken on the morning of Day 4 at 72 hours postdose.

In Part 2 (MAD), patients are expected to be in the study no more than 56 days: up to 28 days for Screening plus up to 28 days for (a) scheduling, (b) 11 days of dosing and associated assessments, and (c) 7 days of follow up after the last dose (or longer if clinically indicated). Patients who are in Screening while dosing is on hold due to SRC meeting may have

participation extended to allow dosing to be scheduled after SRC has convened. While waiting for a cohort to open to patients with LVEF < 25%, these patients may be in Screening up to 12 weeks (if the patient remains stable) while the SRC convenes.

Total time in the study may be longer for patients who participate in both Part 1 (SAD) and Part 2 (MAD).

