4.4.2 Composition of Safety Review Committee

The SRC will be composed of at least 5 members including 2 Sponsor representatives and 3 independent cardiologists. The Sponsor's medical monitor will act as chair of the committee. Sponsor representatives (including the Sponsor's medical monitor) will not be voting members. The 3 independent cardiologists will be the only voting members. Three members including the Sponsor's medical monitor and 2 independent cardiologists need to be present for a quorum, with at least 2 independent cardiologists available for voting. In case of a tie, all 3 independent cardiologists should vote. Other individuals may attend the meeting to share data, but they will not be voting members. All dosing recommendations for individual patients in Period D in SAD Cohort 1 will be discussed with the investigators whose patient it is.

Following review of the existing study data, the SRC may consider recommending changes to the protocol intended to enhance patient safety, data integrity, data robustness, or efficiency of study conduct. As part of the review process, the SRC may need to review the unblinded data. SRC members should consider the possible scenarios and the nature of the decision on study continuation or dose level and what they would consider the appropriate next step (eg, repeat the dose level, continue the dose escalation with reduced dose-escalation steps, or terminate the study).

- All substantial changes to the study protocol will be captured in the meeting minutes, and a protocol amendment will be instituted if needed.
- Nonsubstantial changes to the study approved by the SRC may be implemented immediately without a protocol amendment, and the IRB/Ethics Committee (EC) (as defined in [Section 12.3](#)) will be immediately notified in writing of the change. Examples of these changes are: reducing the dose of the study medication, expanding enrollment, or adjusting timepoints for procedures. Additional blood samples for PK may be obtained but no more than 2 additional timepoints for each dosing period (a maximum increase of 36 mL of blood in total) will be requested. An increase in the number of TTEs, ECGs, or vital sign determinations that may be obtained will also be considered a nonsubstantial change, as these are noninvasive procedures, but no more than 2 additional TTEs will be obtained per dosing period.

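### In Part 2, one matching drug-related SAE on placebo, at any dose step, cancels the compulsory ad hoc SRC review of a first, single such SAE on MYK-491 at a higher dose.

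*Combined protocol and SAP*

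**What the plan says.** Section 4.2.5 makes an ad hoc SRC review compulsory in Part 2 when any of three things happens:

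- "Two patients in a cohort receiving MYK-491 reached individual dose-modification and/or stopping criteria". The same bullet adds that the SRC adjudicates stopping criteria.
- One patient on MYK-491 has an SAE judged related to the drug; the text goes on "including, but not limited to, a SUSAR or coronary ischemic event) that has not also occurred in a patient receiving placebo".
- The Hy's law definition is met in one patient on MYK-491.

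The first trigger is confined to a cohort. The third has no placebo exception. The second has an exception that is not confined to a cohort, dose level, period or count, and the section does not define what counts as the same SAE. A pause is optional even when a trigger fires: "Dosing may be paused until SRC review; eg, in case of drug-related SAEs, SUSAR, or coronary ischemic events".

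For the individual Part 2 patient with a drug-related SAE, Section 4.2.4 says "dosing of a patient must be terminated, AE/SAE forms completed as applicable, and Sponsor should be informed without delay". The SRC appears in that section only for rhythm: "The diagnosis and clinical significance of a new arrhythmia will be adjudicated by the SRC as it relates to this stopping criterion". In Part 1, Section 4.2.1 says instead "dosing of a patient must be suspended, AE/SAE forms completed as applicable, and the event reviewed by the SRC". For ad hoc meetings, Section 4.4.1 refers only to Sections 4.2.2 and 4.2.5.

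**The concern.** The placebo exception decides whether the voting cardiologists must meet before they have seen the event. Suppose a placebo patient in Cohort A or B has an ischemic SAE that the blinded investigator judges drug-related. A first ischemic SAE on MYK-491 in Cohort C, possibly at double the previous dose (the Synopsis allows up to a 2-fold step), then has "also occurred" on placebo in the sense of Section 4.2.5 and no longer convenes the SRC.

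Section 1.3 reports that animal safety testing found dose-limiting toxicity to be exaggerated on-target pharmacology, with myocardial ischemia and heart failure at high doses and after prolonged exposures. A placebo event at a lower dose step says little about whether a first event at a higher step is dose-related. Section 4.1.2 lets several patients in a cohort be dosed at once, so others may still be on treatment when that first event occurs.

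**Working it through.** **Which rules require the SRC to meet for this event.** Take a first, single drug-related SAE on MYK-491 in a higher-dose cohort, after a matching placebo SAE.

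- Single-SAE trigger (4.2.5): switched off by the exception.
- Two-patient trigger (4.2.5): not met by one patient. It is met if another active patient in the cohort has reached any dose-modification or stopping criterion, including the echo-based one in Section 4.2.3, "An increase in the maximal SET > 75 ms on 2 sequential TTE recordings based on site evaluations".
- Hy's law trigger (4.2.5): met only for a hepatic event of that kind.
- Individual stopping rule (4.2.4): dosing ends and the Sponsor is told; SRC review of the SAE is not named.
- Planned reviews (4.4.1): after the first 3 patients in a cohort and after at least 4 to 8 are dosed. These do not depend on the event.

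No rule therefore clearly requires a prompt SRC review of that event.

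**The plan's own figures.** Section 4.1.2 gives 8 patients per cohort, 2 placebo and 6 active. At 3:1, 8 × 3/4 = 6 and 8 × 1/4 = 2; three cohorts give 3 × 8 = 24. These reproduce. The plan gives no event rates and no operating characteristics for the triggers, so every rate below is an assumption, and independence between patients is assumed throughout.

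**Step 1: exception already active before Cohort C.** Count only the double-blind placebo patients in A and B: 2 + 2 = 4. With a rate q per placebo patient of a matching SAE judged drug-related, the chance is 1 − (1 − q)^4.

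- q = 0.5%: 1 − 0.995^4 = 0.0199
- q = 5%: 1 − 0.95^4 = 0.1855

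**Step 2: exactly one of 6 active Cohort C patients has the matching SAE.** With rate p, the chance is 6p(1 − p)^5.

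- p = 10%: 6 × 0.1 × 0.9^5 = 0.3543
- p = 20%: 6 × 0.2 × 0.8^5 = 0.3932

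**Step 3: both together.** 0.0199 × 0.3543 = 0.0070, up to 0.1855 × 0.3932 = 0.0729. This is about 0.7% to 7% if no other active patient meets any criterion.

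**Step 4: allow for the two-patient trigger.** If each of the other five active patients has a 10% or 20% chance of meeting some other criterion, none does with probability 0.9^5 = 0.590 or 0.8^5 = 0.328. The range becomes 0.0070 × 0.328 = 0.0023 to 0.0729 × 0.590 = 0.0431, about 0.2% to 4%. Across Steps 3 and 4 the span is 0.2% to 7%.

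**Step 5: what the count leaves out.** If A and B were each expanded to 24, they would hold 6 + 6 = 12 placebo patients. The exception would then be active with probability 1 − 0.99^12 = 0.114 at q = 1%, and 1 − 0.95^12 = 0.460 at q = 5%. The wording could also reach placebo given in the Days 1–2 run-in, in Part 1 placebo periods, or in the same cohort. Each would raise the figure.

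**The case against.** The opposing case is substantial, and most of it stands as a limit on size.

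- **The precondition is narrow.** The placebo event must itself be a matching SAE judged drug-related under the blind. Sections 5.1 and 5.2 select stable patients and exclude current angina, recent acute coronary syndrome, recent heart failure hospitalization and troponin I above 0.15 ng/mL. Double-blind dosing lasts 7 days. A 5% placebo rate has no support in the documents.
- **The SRC's chair is likely to hear quickly.** The Sponsor is informed without delay (4.2.4), SAEs are reported within 24 hours (10.3.1), and "The Sponsor's medical monitor will act as chair of the committee" (4.4.2). Nothing says the listed triggers are the only grounds for meeting. The chair may therefore call a meeting, but no rule requires it.
- **The SRC adjudicates stopping criteria.** A drug-related SAE is such a criterion, so that sentence in Section 4.2.5 may reach it. But it sits inside the two-patient bullet and does not convene a meeting for one event.
- **Ischemia is among the best-covered events.** Suspected ischemia and troponin elevations go to independent adjudication (4.5), and dosing is withheld while possible ischemia is being understood (9.4.9). Neither is an SRC review of the study.

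A reader might infer that the event would go unseen, that the patient could continue, or that escalation could pass it by. The documents do not support this: the patient stops, and the SRC reviews unblinded summaries and confirms the dose before the next cohort (4.4.1). A reader might also infer the same gap in Part 1. Section 4.2.2 has the same clause, but Section 4.2.1 already sends each such event to the SRC. Nor do the documents describe ischemia as a toxicity observed with MYK-491 in humans; Section 1.3 draws on testing in other species.

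**Conclusion.** The point holds in a limited form. Followed as written, Section 4.2.5 lets one matching placebo SAE, at any dose step and at any time, remove the compulsory prompt SRC review of a first, single matching SAE on MYK-491 at a higher dose. What is lost is that compulsory meeting within a cohort; oversight in general is not lost.

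The gap follows from the wording and does not depend on any rate. Its frequency cannot be measured from the documents. The illustration of about 0.2% to 7% for Cohort C rests on assumed rates of 0.5% to 5% on placebo and 10% to 20% on active drug, independence, planned cohort sizes, and only four placebo patients. It would be higher if other placebo exposure or expanded cohorts count, and the remaining safeguards may catch some of these events. The effect is small, and the priority is low.

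**What to change.** In Section 4.2.5, end the single-SAE trigger at the closing parenthesis by deleting the clause about prior occurrence on placebo. Any drug-related SAE on MYK-491 then convenes the SRC, which can weigh placebo events at the meeting from the unblinded summaries it already receives. The same deletion in Section 4.2.2 is optional, for consistency only.

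The cost is one clause and an occasional extra ad hoc meeting, which could arise in any MAD cohort. In Cohort C alone, the illustration above puts it at about 0.2% to 7%; the other cohorts would add their own small chance. No dose, pause or stopping rule changes.

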4.4 Safety Review Committee

4.4.1 Safety Review Committee Meetings

In Part 1 (SAD), the SRC will meet to review the data after each patient in Cohort 1 has completed the first 3 dosing periods (175 mg, 350 mg, and placebo). The SRC will determine if the subject will receive a third active dose level (open-label Period D) and what the dose should be. The SRC will also meet at the conclusion of Cohort 1 and after all of the patients have completed the study. The SRC will review all relevant data to select the dosing levels for Cohort 2. During Cohort 2 dosing, the SRC will meet to review the data after every 2 to 4 patients have completed all dosing periods. The SRC may recommend dose modification for the remainder of the cohort.

In Part 2 (MAD), the SRC will review data after at least 4 to 8 patients from a cohort have been dosed. The SRC will then confirm the sample size, dose, and regimen (BID or QD) for next MAD Cohort, or may decide to expand current MAD Cohort. Additionally, the SRC will review preliminary safety data after the first 3 patients in each cohort, with LVEF $\geq 25\%$, to decide whether to open cohort enrollment to patients with LVEF < 25%.

A Notification Letter with the rationale for the choice of doses selected by the SRC will be sent to the investigator, who will inform the appropriate Institutional Review Boards (IRBs) as necessary.

Refer to [Section 4.2.2](#) and [Section 4.2.5](#) for criteria leading to ad hoc SRC meetings.

SRC data review will be based on unblinded data summary (see [Section 6.2](#)).

4.4.2 Composition of Safety Review Committee

The SRC will be composed of at least 5 members including 2 Sponsor representatives and 3 independent cardiologists. The Sponsor's medical monitor will act as chair of the committee. Sponsor representatives (including the Sponsor's medical monitor) will not be voting members. The 3 independent cardiologists will be the only voting members. Three members including the Sponsor's medical monitor and 2 independent cardiologists need to be present for a quorum, with at least 2 independent cardiologists available for voting. In case of a tie, all 3 independent cardiologists should vote. Other individuals may attend the meeting to share data, but they will not be voting members. All dosing recommendations for individual patients in Period D in SAD Cohort 1 will be discussed with the investigators whose patient it is.

Following review of the existing study data, the SRC may consider recommending changes to the protocol intended to enhance patient safety, data integrity, data robustness, or efficiency of study conduct. As part of the review process, the SRC may need to review the unblinded data. SRC members should consider the possible scenarios and the nature of the decision on study continuation or dose level and what they would consider the appropriate next step (eg, repeat the dose level, continue the dose escalation with reduced dose-escalation steps, or terminate the study).

- All substantial changes to the study protocol will be captured in the meeting minutes, and a protocol amendment will be instituted if needed.
- Nonsubstantial changes to the study approved by the SRC may be implemented immediately without a protocol amendment, and the IRB/Ethics Committee (EC) (as defined in [Section 12.3](#)) will be immediately notified in writing of the change. Examples of these changes are: reducing the dose of the study medication, expanding enrollment, or adjusting timepoints for procedures. Additional blood samples for PK may be obtained but no more than 2 additional timepoints for each dosing period (a maximum increase of 36 mL of blood in total) will be requested. An increase in the number of TTEs, ECGs, or vital sign determinations that may be obtained will also be considered a nonsubstantial change, as these are noninvasive procedures, but no more than 2 additional TTEs will be obtained per dosing period.

For Part 2 (MAD), the SRC will review data after at least 4 to 8 patients from a cohort have been dosed. The SRC will then confirm the sample size, dose, and regimen (BID or QD) for next MAD Cohort, or may decide to expand current MAD Cohort.

All decisions of the SRC will be documented and provided as appropriate to parties involved with the study.

